B2.1. PTSD, Cognitive Deficit, and ADHD: In our on-going project, we evaluated combat veterans with and without PTSD with Clinician Administered PTSD Scale (CAPS), Conners' Adult ADHD Rating Scales–Self Report: Short Version (CAARS–S:S, score > 65 is regarded clinical significant cognitive impairment; Conner et al 1999). We included 47 participants, 29 PTSD subject (13 with CAARS > 65, 45%) and 18 controls (2 with SAARS > 65, 11%). The results indicated PTSD diagnosis is associated with significantly higher self-reported attentional and executive dysfunction symptoms ($\chi^2 = 5.81, p = 0.16$). This was also evident in the significant correlations between CAPS and CAARS-S:S scores ($R=0.497, p < 0.01$), and CAPS PTSD symptoms ($\beta=.26, t=1.88, p=.05$), and PTSD patient cognitive deficit severity as measured by the CAARS-S:S ($\beta=.59, t=4.81, p<.001, R^2=.34$). These findings further support available literature suggesting that cognitive symptoms associated with PTSD diagnosis are highly correlated with patients' functional outcome.

B2.2. MPH Improves Cognitive Function: Further, we conducted additional preliminary analyses with 8 PTSD individuals with cognitive symptoms who were treated with MPH. Analyses conducted on clinical assessments of patients' PTSD and ADHD symptoms (CAPS and CAARS-S:S) before and after MPH treatment revealed significant reductions in both PTSD and self-reported cognitive deficit symptoms (see Fig1 and Fig2; $F(1, 7) = 22.39, p = .002$).

C. RESEARCH DESIGN AND METHODS:

C1. Overview: The proposed project is a pilot, feasibility double-blind crossover study to investigate the efficacy and safety of ATX with comorbid PTSD/ADHD patients to reduce cognitive symptoms, improve treatment retention and response, and improve patient's activities of daily living. A prospective, 10-week, fixed-dose, randomized, double-blind, placebo-controlled, and cross-over trial of ATX as an adjunctive medication to other therapies will be conducted among veterans with comorbid PTSD/ADHD. The short-duration, crossover design, and blind enable the study to be feasible in both time and funding level. **The Primary Objective** is to assess the efficacy of fixed dose of ATX (80mg) (compared with placebo) in reducing cognitive symptoms in comorbid ADHD/PTSD such that functional

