impairment and treatment retention are both improved, while **The Secondary Objective** is to replicate the our preliminary finding of negative impact of cognitive symptoms of ADHD on PTSD clinical outcomes. **The Tertiary Objective** is to assess the efficacy of ATX in reducing broad spectrum of PTSD symptoms. The proposed study will take 10 weeks and include two phases (**Phase I**: Initial Phase, 5 weeks; **Phase II**: Crossover Phase, 5 weeks). The crossover design was employed to both achieve study objectives while minimizing costs. Each phase consists two periods: **Period I** (week1 in Phase I and week6 in phase II) consist of psychological and physical assessments and placebo lead-in/wash-out, in which subjects take 6 days placebo; **Period II** (weeks 2-5 in Phase I and week7-10 in Phase II) consist of treatment with either atomoxetine 80mg daily or placebo daily). This project will take advantage of established on-going PTSD assessment and treatment clinical trials currently performed at the Ralph H. Johnson VA Medical Center (RHJVAMC) to facilitate recruitment. The proposed 50 veterans with ADHD/PTSD will be recruited from these on-going trials enabling both comprehensive assessment and evaluation of patients' engagement in ongoing PTSD treatments. Subjects will be randomized and assigned by the study investigator ([name]) into crossover group 1 (ATX at Phase I, then placebo at Phase II) or 2 (placebo at Phase I, then ATX at Phase II) with both placebo and medication administered through pharmacy. Subjects and other investigators are thus able to remain blinded to the order of treatment assignment throughout the study. The 1-week interval was based on published pharmacokinetic data for 4 week doses of ATX (*Witcher et al, 2003*). After crossover, patients will be unblinded and data will be cleaned and analyzed. Final follow up will be 30-days after last visit.

C2. Investigational Agent: ATX is a non-stimulant, FDA approved agent for treatment of ADHD. ATX 80mg is the most common adult dose used in ADHD with and without comorbid condition (Adler et al, 2009). In this project, 80 mg ATX and placebo will be prepared in capsules with identical appearance and similar taste by Eli Lilly and Company, Indianapolis, Indiana.

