Concom meds	X	X	X		X	X		
AEs			X			X		

Safety assessments: At each study visit, safety will be assessed by measuring: weight, sitting blood pressure, heart rate, adverse events (except baseline), and use of concomitant medications. Laboratory and EKG assessments will be performed at baseline, one and seven weeks. Anxiety, depression, and suicidal ideation will be assessed with Ham-A, Ham-D, and suicide screen in each of the visits. Compliance will be assessed by pill counts and appointment attendance. Referrals to the Charleston PTSD clinic will be conducted at the final study visit for any remaining PTSD symptoms and the CBT clinic for remaining ADHD symptoms.

Follow-up: The final visit, 30-days after study completion, will include safety assessments, along with follow-up of any unresolved adverse events. This visit will also provide assurance that veterans who participated in this medication study will have adequate follow-up care in the Charleston VAMC PTSD or Mental Health Outpatient Clinic either with continued medication or psychotherapy. This visit may be done over the phone or by mail.

Diagnostic Procedures: After obtaining the informed consent, a trained research assistant will perform the initial interview and administer all of the diagnostic scales to the participants. [name], [name] (MD, Co-Investigator) and [name] (PI) will make the final diagnosis based on all the data collected. The DSM-IV diagnostic criteria will be used to ascertain each phenotype.

Database Management: All collected clinical, demographic, and geographic data will be stored in Research Database Storage in the Charleston VAMC PTSD Program. The genotyping data will be stored in [name] laboratory Research Database. For each patient, the clinical database will provide information as following: age, gender, ethnic origin, medical and psychiatric diagnosis, family history, developmental history, and existence of comorbidity. The genotyping data will be separately entered without knowledge of clinical data. Strict confidentiality is maintained regarding database information, which is secured and for research purposes only. All the specimens from the subjects will be labeled by code at the clinic. Names will not appear on specimens, nor will they be available in the laboratory. The person conducting the genotyping is blind to the clinical profile of the subject. No names or identifiable information will be used in any data presentation.

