Statistical Analyses and Power Estimation: As a pilot feasibility study with double-blind crossover design, the design affords greater power and need for enrollment of fewer subjects. Similar design with this medication has suggested sample size of 40 was sufficient for effect sizes typically observed with this medication in similar populations (Bain et al 2013). To account for patient dropouts, the study will enroll/consent up to 50 patients. This will ensure 40 subjects complete the entire study. This design will allow initial pilot feasibility data, improved control and testing of causation, and greater power in the allotted time-frame and funding level. The primary consideration is difference in outcome between baseline and endpoint with ATX treatment as compared to placebo. The primary outcome measure a priori will be the change in total CAARS-S:S scores, AAQoL-29 and BAARS-IV. Secondary measures include the remaining efficacy and safety measures as delineated above. The primary outcome of interest is the moderating impact of ATX treatment (medication \times ADHD TAU) on treatment response (pre- and post-treatment measures of cognitive symptoms of ADHD and PTSD, functional impairment in daily living domains, and global functioning). A mixed model, repeated-measures multivariate analysis of variance with pre- and post-ADHD TAU treatment ADHD symptoms, functioning, and global functioning entered as repeated measures; and ATX treatment entered as the between factors. Pre-treatment PTSD severity scores (CAPS) will also be entered into the model as a potential explanatory covariate. Simple slopes using repeated measures ANOVA will be used to probe significant interactions

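### The statistical section states two conflicting primary effects, and one rests on an undefined ADHD TAU that the trial does not assign or schedule

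*Combined protocol and SAP*

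**What the plan says.** All references are to the combined protocol and SAP. The paragraph on statistical analyses and power in C3 describes the primary effect twice.

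- First: "The primary consideration is difference in outcome between baseline and endpoint with ATX treatment as compared to placebo". This agrees with C1, where the Primary Objective "is to assess the efficacy of fixed dose of ATX (80mg) (compared with placebo) in reducing cognitive symptoms".
- Second: "The primary outcome of interest is the moderating impact of ATX treatment", explained in brackets as medication multiplied by ADHD TAU.

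The model sentence follows the second description. It has "pre- and post-ADHD TAU treatment ADHD symptoms, functioning, and global functioning entered as repeated measures" and "ATX treatment entered as the between factors", with pre-treatment CAPS as a covariate. Simple slopes are to be used to probe significant interactions.

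The design is set out in C1. Patients are randomised to "crossover group 1 (ATX at Phase I, then placebo at Phase II") or to the reverse order. The trial uses "ATX as an adjunctive medication to other therapies", and those therapies are not specified. The term TAU occurs only in the statistical paragraph, twice, and is not spelled out. The one piece of ADHD care outside study drug that the plan names is a referral, made "at the final study visit for any remaining PTSD symptoms and the CBT clinic for remaining ADHD symptoms" (C3, Safety assessments).

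**The concern.** A moderation effect needs a moderator that takes more than one value and is recorded. A pre/post factor needs dated occasions. The plan supplies neither for ADHD TAU, yet this is the effect that it calls the outcome of interest and carries into the model.

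An analyst working from this text would have to choose between the two descriptions and then decide what TAU means. C1 places unblinding before data cleaning and analysis, so the choice could be made with treatment order known. One possible choice, dividing patients by whatever ADHD care they happen to receive, answers a different question from the Primary Objective.

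**Working it through.** No figure in the plan can be reproduced on this point. The sample size (40 completers, up to 50 enrolled) comes without alpha, power, effect size or SD. The check is one of structure.

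**1. Where ADHD TAU could enter the design**

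- Randomisation (C1): two ATX/placebo sequences; no TAU arm, stratum or period.
- Background treatment: C1 speaks of evaluating engagement in PTSD treatment, not ADHD treatment. C3 (PTSD Medication Stabilization) asks patients to keep current medication doses, so that treatment neither starts at baseline nor ends at endpoint.
- Table 1: no row for TAU or psychotherapy, and no TAU start or end. Concomitant medications are marked at five visits, and the safety text says every visit. ADHD drug use could be derived from these records; non-drug ADHD care and the timing of TAU could not.
- Referral for remaining ADHD symptoms: at the final visit, after both treatment phases.

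**2. Is the interaction estimable?**

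Take 40 patients, two phases and a pre and post value in each. Use six columns: intercept, medication, period, sequence, pre/post, and medication × pre/post. Then add three: TAU, medication × TAU, and medication × TAU × pre/post.

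- Without TAU: rank 6 of 6, so the ATX-placebo effects are estimable.
- TAU the same for everyone: rank 6 of 9, so all three TAU terms are aliased.
- TAU varying between patients and recorded: rank 9 of 9. The interaction is estimable, but TAU is not randomised.

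**3. If ADHD TAU means time within a phase**

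The interaction becomes medication × pre/post, the ATX-placebo difference in change. That needs a pre value in each phase. In Table 1, CAARS-S:S is taken at every visit. BAARS-IV and AAQoL-29 are taken at baseline, W5 and W10, but not at W6, the start of Phase II.

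Let A and P be mean end-of-phase scores on ATX and placebo, and B the baseline mean. Assume no carryover and equal sequence groups.

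W5 as the Phase II pre value:

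- ATX first: (A − B) − (P − A) = 2A − P − B
- Placebo first: (A − P) − (P − B) = A − 2P + B
- Average: (3A − 3P)/2 = 1.5 (A − P)

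Baseline as the pre value in both phases: each sequence gives (A − B) − (P − B) = A − P.

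Additive period effects p1 (W5) and p2 (W10) cancel in the average. Under the W5 choice they add 2p1 − p2 in one sequence and p2 − 2p1 in the other. Under the baseline choice they add p1 − p2 and p2 − p1.

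The same data therefore estimate 1.5 or 1.0 times the drug difference, depending on a choice that the text leaves open. A direct comparison of end-of-phase scores at W5 and W10 gives A − P and needs no Phase II pre value.

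**4. ATX as a between factor**

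A between-patient factor has one value per patient. Here every patient who completes both phases receives ATX and placebo, so the model sentence does not describe the crossover under either reading of TAU.

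**The case against.** The strongest reply is that ADHD TAU is only a loose label for the pre/post occasions. The model sentence contains no factor for TAU present or absent, and the same paragraph describes response through measures taken before and after treatment. On that reading the interaction is medication × time, which is estimable and is the ATX-placebo difference in change. The paragraph also names ATX against placebo outright, in agreement with C1.

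Much of this stands. A reader might infer that the plan contains no estimable drug effect, or that the interaction has no degrees of freedom. The documents do not support either. The ATX-placebo contrast is stated and estimable. An undefined factor is not necessarily constant: eligibility does not expressly exclude current ADHD treatment, and ATX is added to other therapies, so background care could vary. A reader might also infer that ADHD care goes wholly unrecorded, but concomitant medications are captured. Nor can a loss of power be attached to the plan, because it proposes no split by ADHD care and gives no inputs for one.

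The reply does not remove the conflict. The text speaks of moderation, writes the product with ADHD TAU and plans simple slopes; nothing says that time is meant. If time is meant, the wrong factor is named, the Phase II pre value is open for two of the three primary measures, and ATX is still coded as a between factor. That the study is a pilot does not settle which effect is primary.

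**Conclusion.** Wrong as written. The plan gives two primary effects that are not the same. The ATX-placebo contrast fits the Primary Objective. The ADHD TAU moderation cannot be estimated from the design as described unless ADHD care happens to vary and is reconstructed, and it would then be an unrandomised comparison of subgroups.

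No arithmetic error is alleged. The consequence is an unsettled estimand. Even under the reading kindest to the text, the choice of Phase II pre value moves the estimate for BAARS-IV and AAQoL-29 between 1.0 and 1.5 times the true difference. That factor assumes equal sequence groups, no carryover and additive period effects. The estimability result assumes that TAU is constant or unrecorded; the documents do not say whether it varies. This goes beyond missing detail, because following the model sentence would give either an analysis that cannot be run or one that does not match a crossover.

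**What to change.** In the statistical paragraph of C3:

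1. Delete both uses of ADHD TAU.
2. State one primary effect: the mean within-patient difference, ATX minus placebo, in scores at the end of each treatment phase (W5 and W10). Table 1 already schedules all three primary measures at both visits.
3. Replace the between-factor wording with ATX as a within-patient factor, with period and sequence terms.
4. Reword the primary-consideration sentence, which now refers to baseline and endpoint, so that it describes the same contrast.
5. If concurrent ADHD care is of interest, derive what the concomitant medication records allow and list it as an exploratory modifier only.

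Deleting ADHD TAU alone is not enough, because the between-factor coding and the baseline-to-endpoint sentence would still disagree with the within-patient effect. The cost is SAP wording; no new visits or data are needed.

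### The primary model treats ATX as a between-patient factor in a crossover where every completer takes both ATX and placebo, so it gives up the crossover's power or misstates the standard error

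*Combined protocol and SAP*

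**What the plan says.** Section C1 (Overview) randomises patients to the order of treatment: "crossover group 1 (ATX at Phase I, then placebo at Phase II) or 2 (placebo at Phase I, then ATX at Phase II". Each completer therefore receives both treatments, and only sequence differs between patients.

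The Statistical Analyses and Power Estimation paragraph of C3 relies on this. It says that "the design affords greater power and need for enrollment of fewer subjects", and adds a cited precedent: "Similar design with this medication has suggested sample size of 40 was sufficient". Up to 50 patients are enrolled so that 40 complete.

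The same paragraph sets the comparison: "The primary consideration is difference in outcome between baseline and endpoint with ATX treatment as compared to placebo". The repeated part of the model is given as "A mixed model, repeated-measures multivariate analysis of variance with pre- and post-ADHD TAU treatment ADHD symptoms, functioning, and global functioning entered as repeated measures". The drug comparison is not part of that repeated structure; its role is described in these words: "and ATX treatment entered as the between factors". The one covariate is baseline PTSD severity: "Pre-treatment PTSD severity scores (CAPS) will also be entered into the model as a potential explanatory covariate". No period term, sequence term or link between a patient's two phases appears, and the Phase II baseline is not defined.

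**The concern.** In this design ATX versus placebo is a within-patient contrast. A model with pre/post within and ATX between is the usual analysis of a parallel-group trial. Calling it a mixed model does not change that, because the factors it names are those of a parallel-group trial.

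An analyst who follows the text has two options:

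- **Phase I only.** ATX really is a between-patient factor there, with 20 patients per arm. The test is valid, but Phase II is discarded.
- **Both phases stacked.** This gives 40 ATX records and 40 placebo records treated as coming from 80 different patients. The correlation within patients is ignored, so the standard error is generally wrong.

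Either way, the primary efficacy test does not deliver the efficiency that the sample size depends on. The missing period term is a further, smaller risk. A time trend, such as regression toward the mean after entry on CAARS-S:S > 65 or response to concurrent PTSD care, can leak into the treatment estimate if dropout unbalances the sequences.

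**Working it through.** **Inputs.** From the documents: 40 completers, 50 enrolled, two sequences (taken as 20 each). Not in the documents, so assumed: two-sided alpha 0.05, 80% power, effect d in SD units, and equal correlation rho between any two visits. Below, r is the correlation between a patient's two phase outcomes.

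**The plan's own figure.** The 40 cannot be reproduced, because alpha, power, effect size, SD and correlation are not stated. The enrolment step does reproduce with 20% dropout: 40/(1 − 0.20) = 50.

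**What 40 completers can detect.** Within-patient analysis: d = (1.960 + 0.842) × √(2(1 − r)/40). Between-patient analysis, 20 versus 20: d = 2.802 × √(2/20) = 0.89. The power of 20 versus 20 at the crossover's detectable effect is Φ(d/√(2/20) − 1.960). The variance ratio, parallel to crossover, is 2/(1 − r).

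| r | Detectable d, crossover | Variance ratio | Power of 20 vs 20 at that d | Total N a parallel trial needs |
|---|---|---|---|---|
| 0 | 0.63 | 2.0 | 51% | 82 |
| 0.3 | 0.52 | 2.9 | 38% | 116 |
| 0.5 | 0.44 | 4.0 | 29% | 160 |
| 0.7 | 0.34 | 6.7 | 19% | 268 |

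With t rather than normal quantiles, the r = 0.5 row gives 0.45 SD for the crossover, against 0.91 SD for 20 versus 20.

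**Phase I only, on change scores.** The plan analyses change from baseline. Under equal correlation a change has variance 2(1 − rho), so the 20-versus-20 variance is 2(1 − rho) × 2/20. The crossover variance is 2(1 − rho)/40. The ratio is 4 whatever rho is, so power is Φ(2.802/2 − 1.960) = Φ(−0.559) = 29%.

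**Stacking.** The stacked standard error is 1/√(1 − r) times the true one, and the false-positive rate is 2(1 − Φ(1.960/√(1 − r))). Under equal correlation, r depends only on the baseline chosen:

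- **Screening baseline for both phases.** The two changes share one baseline. Their covariance is 1 − rho and their variance 2(1 − rho), so r = +0.5. The ratio is 1/√0.5 = 1.41. At rho = 0.5 the reported standard error is √(1 × 2/40) = 0.224, against a true √(1/40) = 0.158. The false-positive rate is 2(1 − Φ(2.77)) = 0.006 (simulated 0.006 to 0.007). Simulated power at the effect the crossover detects with about 80% power is 51 to 53%.
- **Week 5 as the Phase II baseline.** Week 5 ends one change and starts the next, so the covariance is −(1 − rho) and r = −0.5. The ratio is 1/√1.5 = 0.82. At rho = 0.5 the reported standard error is 0.224, against a true √(3/40) = 0.274. The false-positive rate is 2(1 − Φ(1.60)) = 0.11 (simulated 0.108 to 0.116).
- **Weeks 1 and 6 as phase-specific baselines.** The two changes are uncorrelated, so r = 0. The false-positive rate is about nominal (simulated 0.049 to 0.054), but power is still only about 52%.

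A proper crossover analysis held a false-positive rate of 0.049 to 0.054 in simulation.

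**Which baselines exist.** In Table 1, CAARS-S:S is measured at weeks 1 and 6. BAARS and AAQoL-29 have only screening, week 5 and week 10 within the crossover. For two of the three primary outcomes, the only available Phase II baselines are therefore the two that give a wrong standard error when stacked.

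**Period term.** Assume a linear trend of 1 SD from baseline to week 10, 23/17 completers by sequence, and a screening baseline. The ATX mean shifts by (23 × 0.5 + 17 × 1)/40 = 0.7125 and the placebo mean by (17 × 0.5 + 23 × 1)/40 = 0.7875. The bias is 0.075 SD in size with no drug effect.

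**The case against.** Four points deserve an answer.

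- **A workable reading exists.** If the between factor were sequence, the ATX effect would be the sequence-by-period interaction, which is a correct crossover test. Simulated on weeks 5 and 10, it has a false-positive rate of 0.048 to 0.054 and 80% power. But the plan says ATX treatment, not sequence, and repeats only pre/post, so this reading replaces the text rather than interpreting it.
- **Stacking is not always invalid.** With week 1 and week 6 baselines the standard error for CAARS-S:S is about right. This stands. It still loses power, the plan does not specify it, and it is impossible for the other two primary outcomes.
- **The magnitudes rest on assumptions.** This also stands. The documents give none of the design parameters, and even the direction of the standard-error mistake depends on an undefined baseline. The trend and the 23/17 split are illustrative. With equal-length phases and phase-specific baselines, a linear trend would produce no shift.
- **The sample size has another support, and this is a pilot.** The plan also cites a similar-design study, whose analysis and effect size cannot be seen from these documents. That cannot justify a between-patient analysis here. Pilot status softens the point only a little, because the stated primary objective is efficacy against placebo.

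**Conclusion.** The concern holds, and the model must be corrected before analysis. The contradiction between C1 and the statistical section of C3 is plain in the text and needs no assumption. The size does depend on assumptions: 40 completers split evenly, two-sided 5%, and equal correlation between visits. Power falls from 80% to about 29% if only Phase I changes are used (19 to 51% on endpoint values for r from 0.7 to 0). It falls to about 51 to 53% if phases are stacked on screening. The false-positive rate when stacking is about 0.6% with a screening baseline and about 11% with week 5 as the Phase II baseline. Bias from the missing period term is secondary and arises only if the sequences become unbalanced.

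**What to change.** Delete the between-factor wording and specify, for each primary outcome, a linear mixed model on the two end-of-phase values (weeks 5 and 10). It should have fixed effects for treatment, period and sequence, a random patient effect, and the screening value of the outcome as covariate. Baseline CAPS can stay as a further covariate. The primary test is the within-patient ATX minus placebo contrast. Patients who complete only Phase I should be included.

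The plan should also state:

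- which baseline defines change in each phase, wherever change is still reported;
- what becomes of the multivariate test and the medication-by-ADHD-TAU term, since the new model replaces the first and does not contain the second;
- the alpha, power, effect size and within-patient SD or correlation behind the 40 completers.

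The cost is analysis-plan wording. No new data, visits or patients are needed.
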